5.0 Inclusion and Exclusion Criteria/ Study Population

Study Population

Participants in the proposed study will be child/caregiver dyads seeking outpatient burn care at MUSC. Caregivers will be parents or legal guardians of the child participant. We expect that females and minorities will be very well represented in this study based on demographic data collected during our retrospective review of pilot data. We anticipate that 40% of youth recruited into the study will be girls. Caregivers' age may vary but the majority will be 25-45 years. Additionally, women are expected to comprise the majority (85%) of participating caregivers. Because mothers are more often the caregivers of injured patients, it is anticipated that more women will be recruited as caregiver providers than men. Participants of all racial/ethnic backgrounds will be eligible for this study. We estimate that Black or African American children and providers will comprise approximately than 50% of our sample. Given the low prevalence of individuals of Hispanic ethnicity in SC (5%) and data from our pilot study, we estimate that our sample will be comprised of approximately 5% of Hispanic youth in this study.

Inclusion Criteria for child/caregiver dyads

Participants will be eligible for enrollment if:

- (1) the patient (child) is < 18 years of age;
- (2) the patient is diagnosed with a partial thickness burn between <1% TBSA – 20% TBSA by a pediatric burn surgeon;

- (3) the burn is being treated with advanced burn dressing therapy (e.g., SilvadeneTM, PolysporinTM, ActicoatTM, MepilexTM, or MepitelTM) or skin substitutes;
- (4) the burn is evaluated by the MUSC burn team within 72 hours of injury;
- (5) the patient's caregiver (parent or legal guardian) is able to speak, hear, and understand English, as determined during study recruitment procedures;
- (6) the patient/caregiver owns and is capable of using a smart device (an Android or iOS smartphone) with permission to download TOBI app from the Google Store or AppStore;
- (7) able to comply with outpatient clinic visits.

There are no exclusion criteria. All participants who meet inclusion criteria would be eligible to participate in the study.

6.0 Number of Subjects

We will recruit 64 child/caregiver dyads (for a total of 128 people) seeking outpatient treatment at MUSC for acute burn injury.

Consistent with the intent of a feasibility RCT, sample size for this study was determined for pragmatic reasons rather than through formal power calculation. Following the recommendations by Kraemer et al. [73] as well as the CONSORT 2010 statement extension to randomized pilot and feasibility trials [74] the purpose of feasibility/pilot studies is to test recruitment processes, feasibility of the intervention and measurement as well as training protocols, data collection, and data quality control, storage and retrieval processes. Further, Kraemer et al. advise that effect size estimates obtained from pilot studies have insufficient accuracy as useful input for sample size determination for future study design.

We anticipate high feasibility of recruitment of 64 pediatric patient/caregiver dyads with partial thickness burns over 24 months. Our TOBI pilot included recruitment of 32 patient/caregiver dyads, and this recruitment was completed over 9 months with minimal infrastructure. With ~200 outpatient pediatric partial thickness burns cases per year at MUSC and our track record of enrolling participants into clinical studies (including TOBI pilot), an enrollment of ~25% of this sample of ~275 is highly feasible. We had a 74% participation rate in the TOBI pilot, 3-4 times higher than what is needed to meet proposed targets.

7.0 Setting

The proposed study will be conducted at the MUSC campus and remotely via telephone/videoconference and TOBI. Participants will be recruited into the study during their initial visit to the MUSC outpatient burn clinic, hospital floor, or pediatric emergency room for the treatment of pediatric burns. Patients that visit and get discharged from the pediatric emergency room in the after-hours or patients that were missed due to staff unavailability will be contacted by phone by a clinical care team member within 72 hours. Informed consent with caregivers and assent with children, when applicable, will be conducted in a private room at Shawn Jenkins Children's Hospital or virtually at the patient's private location using secure videoconferencing.

8.0 Recruitment Methods

The MUSC Pediatric Burn program provides the only tertiary burn care in the state to >200 pediatric patients annually. We will use a convenience sampling strategy to recruit 64 patient/caregiver dyads who have undergone a face-to-face (FTF) clinical encounter with an MUSC burn professional at the outpatient burn clinic, the hospital floor, or the pediatric emergency room. Patients will be seen in person and prescribed therapy by our burn experts in our standard practice. Patient/caregiver dyads who meet the inclusion criteria will be considered eligible for enrollment.

Recruitment will be initiated in-person in MUSC's outpatient burn clinic setting, the hospital floor, or pediatric emergency room. Patients/caregivers that visit and get discharged from the pediatric emergency room in the after-hours or patients that were missed due to staff unavailability will be contacted by phone by a member of the clinical care team within 72 hours. Once a possible study candidate dyad is identified, patients will be asked about participating in the feasibility RCT and the study will be explained by study staff, either in-person or by phone/virtually. Study staff will include members of the clinical care team (e.g., burn nurse, physician) and research staff (e.g., clinical trial coordinator). Initial mention of the study will occur with a member of the clinical care team who is also a research team member. If the caregiver expresses interest, study staff will screen potential participants for eligibility and proceed with reviewing informed consent (and assent if applicable) and will address the risks and benefits of the study. For potential participants contacted by phone, the review of informed consent will occur virtually. If potential participants indicate further interest in the study, study staff will obtain written or electronic informed consent from caregivers and assent from children, if applicable. After enrollment, patient/caregiver dyads will be randomized. The randomization scheme will yield at least 32 patients per treatment group.

Pace of patient referral and recruitment will be tracked on a weekly basis by the project team to anticipate, identify, and address potential challenges with recruitment. Our TOBI pilot included recruitment of 32 patient/caregiver dyads, and this recruitment was completed over 9 months with minimal infrastructure. Based on our TOBI pilot recruitment rate, we anticipate high feasibility of recruitment of 64 pediatric patient/caregiver dyads with partial thickness burns over 24 months.

9.0 Consent Process

Informed consent will be obtained from caregivers with legal custody and assent will be obtained from child patients who are 12 years old or older.

Prospective participants will be informed about the study during their FTF clinical encounter with an MUSC burn professional at the outpatient burn clinic, on the hospital floor, or in pediatric emergency room. Patients/caregivers that visit and get discharged from the pediatric emergency room in the after-hours or patients that were missed due to staff unavailability will be contacted by phone and informed about the study by a clinical care team member within 72 hours. Participants will be informed about the project's rationale geared towards evaluating two treatment delivery modalities for burns (TOBI and FTF). If they express interest in the study, study personnel will invite them to complete an informed consent/assent in a private room or virtually at a patient's private location using secure videoconferencing. The study team member will summarize the content of the

informed consent/assent form and ask for any questions. Alternatives to participating in the proposed research will be mentioned; they include continued treatment outside of the study by the health provider who referred them to the study and with whom patients have established care. We will be amendable to patients' preferences. Patients will be informed that declining to serve as a participant in this study will not influence or compromise the quality of their care. If participants express continued interest, study personnel will provide an opportunity for participants (caregivers and children over the age of 12) to review the consent and will obtain written or electronic signature from caregivers and assent from patients who are at least 12 years old. For electronic consent, participants will be invited to join a secure Doxy conference call and will complete an electronic informed consent via Doxy. Participants may also complete electronic informed consent via a REDCap e-consent link (e.g., if Doxy is not working). They will have an opportunity to read it and ask questions. The person obtaining the consent will then sign it in writing or electronically and provide a hard copy or email an electronic copy to the participant via secure MUSC email. Any participant who does not meet study inclusion criteria (as reviewed during the informed consent process) or does not agree to participate, will be excused from the study.

10.0 Study Design / Methods

The RCT will include 64 patient/caregiver dyads recruited from the MUSC outpatient burn clinic, hospital floor, or pediatric emergency room, randomized to burn care enhanced with TOBI (n=32) or FTF standard care (n=32). After obtaining informed consent, the research staff will create a new patient record in the REDCap database and assist (if needed) the caregiver in completing the initial questionnaire battery using the REDCap survey. The baseline questionnaires, completed by the caregiver, will include the demographics form, measures about attitudes toward telemedicine, perception of healthcare access, affect, depression, anxiety, self-efficacy, and peritraumatic distress (see measures attached). All PHI will be protected by a study ID to promote confidentiality. The family will receive a ClinCard at the beginning of the study which works like a bank debit card and can be used to purchase goods or services everywhere Debit MasterCard is accepted. Each time they receive payment for participation in this study, the money will be added to the card. Families will receive \$20 for completion of baseline assessment.

At the completion of questionnaires, caregivers will be randomly assigned to treatment conditions. Stratified permuted block randomization will be used to assign patients to either the burn care enhanced with TOBI or FTF care only (32 dyads per arm). Assignment will be stratified by provider to ensure balanced enrollment across the treatment arms regardless of numbers enrolled per provider. To minimize the likelihood that the blind will be broken, i.e. the next treatment assignment can be guessed, the block size will be varied.

Chart review will be conducted within approximately 72 hours of enrollment and data will be recorded in a chart review checklist and subsequently transferred into the database (e.g., burn mechanism, % TBSA, burn location, burn depth, date of burn injury, time to medical treatment, type of first clinical encounter [burn outpatient vs. emergency department vs. hospital discharge], and type of dressing).

Patients randomized to FTF will undergo standard burn care including a return follow-up in the burn clinic on a routine basis as prescribed by the clinical burn team (e.g., at least once per week) until the burn has healed. Healing is defined as greater than 95% epithelialization of the burn wound. This will be determined by a clinician.

Patients randomized to burn care enhanced with TOBI will be given instructions and will be aided in downloading TOBI onto their smartphones. Patients with TOBI will be able to use standard FTF care as well. They will demonstrate an ability to use the various components of TOBI during initial visit and enrollment and will be explained how to contact the burn team through the hospital paging operator if TOBI is unavailable. Similar to the FTF group, they will be given oral and written instructions about standard burn care with routine clinical care delivered via TOBI, including a plan to interface with the burn clinicians (text messaging, videoconferencing, or image transfer) on a routine basis. TOBI patients will be scheduled for weekly videoconferencing encounters through the app until the burn has healed. Patients will be asked to come in-person if would complications are noted by a clinician (e.g., non-healing, infection). If technological problems with TOBI are encountered (e.g., video stops working), providers may switch to another secure telehealth platform to provide the necessary care and will document technology issues appropriately, as part of feasibility assessment.

Clinical data will be collected on case report forms by the clinical care team (e.g., burn nurse, physician) and entered into the REDCap database in a coded manner by a research assistant (who is blind to the treatment condition to reduce bias during data entry) at clinically determined intervals per routine care based on clinical judgment with TOBI or FTF (see table below). The duration and number of clinical encounters for both conditions will be guided by best clinical practice and each patient's needs. On average, most burns that meet the study eligibility criteria require 2-5 visits and heal within 2-4 weeks. Case report forms will be generated with study ID only, with no identifiable PHI in order to protect patient's privacy. Data collected at intervals will include adherence to prescribed wound care, change in therapy, wound complications, day of healing, pain scores, sleep problems, unexpected return to clinic or emergency room (see Clinical Case Report Form attached). App metrics, such as number of videoconferences, number of text-messages, number of photos, and scripted messages by burn professional will be recorded by the app software and exported at the end of the study. Images of wounds will not be stored for the purposes of this study. They may be uploaded by clinical care team members into the patient's medical record as part of standard care procedures (outside of the study). Adherence to therapy will be defined as parent/patient performance of prescribed wound care through the end of treatment. Overall compliance with therapy is defined as documentation of healed burn through TOBI or FTF. Clinical data collection will continue until 1 month after the burn is diagnosed as healed by a burn physician in either condition (FTF or TOBI).

At 1-month, caregivers will be asked to complete the post-treatment questionnaires by phone or virtually using the REDCap survey, using a public link and study ID to identify their survey. This assessment will include measures about attitudes toward telemedicine, perception of healthcare access, affect, depression, anxiety, perceived stress, posttraumatic growth, treatment satisfaction, and app feasibility (TOBI only group) (see measures attached). Collected data will be entered into REDCap by the study staff. Overall, participation rate will be recorded. Families will receive \$30 following completion of post-treatment assessment.

Data analyses will be performed by [name] and study coordinator at the completion of the study in aggregate in a blinded fashion to prevent bias as much as possible. Quantitative questionnaire and case report form data will be exported from REDCap and

analyzed using statistical software (e.g., SPSS). [name] will oversee [name] and the study coordinator in all data analyses.

TOBI	Data Collected	Enrollment	TOBI Video Visit 1	TOBI Video Visit 2	TOBI Video Visit 3	TOBI Video Visit 4	TOBI Video Visit X (possible)	End of therapy (1 month FU)
	Demographics Form	X						
	Chart review data (e.g., burn mechanism, % TBSA, burn location, burn depth, date of burn injury, time to medical treatment, type of first clinical encounter [burn outpatient vs. emergency department vs. hospital discharge], and type of dressing)	X within 72 hrs						
	Caregiver measures: - Attitudes toward telemedicine / technology - Perception of healthcare access - PANAS (affect) - PROMIS-Depression - PROMIS-Anxiety	X						X
	Caregiver measures: - PROMIS-General-Self-Efficacy - PROMIS-Self-Efficacy-Manage-Emotions - Peritraumatic Distress Inventory	X						
	Caregiver measures: - Perceived Stress Scale - Posttraumatic Growth Inventory							X
	Case Report Form: - Clinical endpoints, including pain score, healing, infection, change in therapy, adherence, sleep, unexpected return to ED/clinic	X	X	X	X	X		
	Caregiver satisfaction & usability surveys: - Satisfaction questionnaire - MAUQ (app usability) – TOBI only							X
	Post-treatment data: - Adherence to treatment - Total # of FTF visits - Total # of TOBI visits - Total travel time - Direct cost to patient/caregiver - Return to work/school date							X
	App metrics (# of video-conferences, messages, & photos) – TOBI only							X
FTF	Data Collected	Enrollment	Clinic Visit 1 (date)	Clinic visit 2 (date)	Clinic visit 3 (date)	Clinic Visit 4 (date)	Clinic Visit (possible)	End of therapy (1 month FU)

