Aim 1: Assess feasibility of the proposed RCT methodology, including recruitment, participation and attrition, treatment fidelity, safety, and problems associated with equipment.

Aim 2: Obtain estimates of variability for the primary outcome measures: time to treatment of wound complication (e.g., infection, pain, non-healing), patient's sleep, therapy adherence, and FTF clinical visits. These variability estimates are needed to calculate sample size for a subsequent larger, adequately powered RCT to compare the effects of the TOBI intervention with FTF alone.

Aim 3: Examine factors related to caregiver attitudes toward telemedicine and access to health care, as well as caregiver stress, self-efficacy, and well-being in relation to treatment outcomes. Because caregivers randomized to TOBI will be the ones delivering burn treatment under the guidance of a provider through the app, they may experience elevated stress levels and anxiety, and their self-efficacy may influence treatment. Assessing these domains will strengthen our understanding of treatment utilization and outcomes as a function of caregivers' psychological factors. We also would like to assess post-injury caregiver adjustment from a more positive perspective (e.g., personal strengths, relating to others in times of need, spiritual change, appreciation of life), a construct that is conspicuously scarce in the scientific literature on caregivers of burn-injured children. Treatment feasibility and satisfaction will also be assessed.

The proposed mHealth intervention may (1) improve the quality of and access to expert burn care for pediatric surgical patients and their families and (2) relieve the burden on burn providers by allowing them to remotely direct treatment in the patient's home. TOBI has significant clinical utility and strong potential to influence access to care and alter the doctor-patient relationship, enabling healthcare providers to prescribe the right intervention at the right dose at the right time for each patient. Findings from this study will demonstrate the feasibility of testing a scalable, low-cost intervention in a multicenter RCT.

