focus on variability and precision of estimates rather than magnitude of effect sizes. 95% confidence intervals (CIs) of the difference in mean days to healing (or treatment change/infection) between interventions will be obtained. In addition, survival distributions and their 95% CIs will be obtained for each intervention arm using the Kaplan-Meier product limit method. Further, 95% CIs for hazard ratios will be obtained using Cox proportional hazards regression to model time to healing (treatment change) as a function of the intervention. In the future RCT, generalized linear mixed models (GLMM) will be used to obtain estimates of the variances of the clinical outcomes and the covariance structure of longitudinal measures as critical input information for determination of sample size (and hence adequate power) [82, 83]. Frequency distributions of AEs and SAEs will be used to characterize each intervention group. Analyses of caregiver data will include pre- and post-treatment group differences (TOBI vs. FTF) to understand factors related to caregiver well-being and adjustment following mHealth burn treatment and possible predictors of outcomes. These analyses may include mixed design repeated measures analyses of variance (ANOVAs) and regressions.

When the study is concluded, after 6 years all records related to the study will be destroyed. Furthermore, all staff will sign confidentiality agreements, and training sessions will emphasize the critical importance of confidentiality. The likelihood that these methods will effectively protect the confidentiality of participants is considered to be extremely high. Based on our experience with previous research projects, it is believed that these procedures will be effective in protecting confidentiality of subjects and minimizing any potential risk from participation.

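### Perceived stress is measured only at 1 month, so the pre/post arm comparison planned for caregiver data cannot be made for stress, which Aim 3 names as a concern for TOBI caregivers

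*Combined protocol and SAP*

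**What the plan says.** All references are to the Combined protocol and SAP.

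- **Aim 3 (Section 1.0)** covers caregiver stress, self-efficacy and well-being in relation to treatment outcomes. One reason given for measuring them in the TOBI arm is that "they may experience elevated stress levels and anxiety". The objective paragraph of the same section adds that these factors are assessed to see whether they bear on use of services and on outcomes.
- **Baseline battery (Section 10.0)**, completed before randomisation: demographics, attitudes toward telemedicine, then "perception of healthcare access, affect, depression, anxiety, self-efficacy, and peritraumatic distress (see measures attached". Perceived stress is not listed.
- **1-month battery (Section 10.0)**: attitudes, access, affect, depression and anxiety again, then "perceived stress, posttraumatic growth, treatment satisfaction", with app feasibility for the TOBI arm.
- **Schedule table (Section 10.0)**: the row "Perceived Stress Scale - Posttraumatic Growth Inventory" is marked only at the end-of-therapy (1-month) visit. The row "PROMIS-General-Self-Efficacy - PROMIS-Self-Efficacy-Manage-Emotions - Peritraumatic Distress Inventory" is marked only at enrollment.
- **Analysis (Section 11.0)**: "Analyses of caregiver data will include pre- and post-treatment group differences (TOBI vs. FTF"), in order to understand caregiver adjustment and possible predictors of outcomes. Repeated-measures ANOVA and regressions are named as models that may be used.
- **Endpoints (Section 4.0)**: distress and stress appear as a single secondary item.

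**The concern.** The analysis plan promises pre- and post-treatment arm differences for caregiver data and excepts no measure. A change score, a time-by-arm contrast or a baseline-adjusted comparison needs the same instrument at both times, and the Perceived Stress Scale is given once. Anxiety, which Aim 3 names beside stress as a possible burden on TOBI caregivers, is measured twice.

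Two uses of the stress data are affected. The arm comparison loses the precision that a baseline score would bring. The predictor question is weakened as well: a score first taken at the end-of-therapy follow-up comes after most of the clinical course, so high stress could be a result of a difficult course and not a forerunner of it.

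**Working it through.** The plan states no figure to reproduce. Section 6.0 sets the sample size on pragmatic grounds, and no SD, effect size or correlation is given.

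**Step 1: time points per construct**, from the two lists and the table in Section 10.0.

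| Construct | Baseline | 1 month | Pre/post estimable |
|---|---|---|---|
| Attitudes to telemedicine | yes | yes | yes |
| Healthcare access | yes | yes | yes |
| Affect (PANAS) | yes | yes | yes |
| Depression | yes | yes | yes |
| Anxiety | yes | yes | yes |
| Perceived stress | no | yes | no |
| Posttraumatic growth | no | yes | no |
| Self-efficacy | yes | no | no |
| Peritraumatic distress | yes | no | no |

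Five constructs support the analysis and four do not. Of the four, posttraumatic growth concerns adjustment after the injury, so a single later measurement is natural. Self-efficacy at baseline can still serve as a predictor, which is how Aim 3 describes it. The Peritraumatic Distress Inventory and the Perceived Stress Scale are different instruments, each given once, so together they do not form a repeated measure. That leaves stress as the construct whose stated role the schedule does not support.

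**Step 2: what a baseline score would add.** Inputs: 32 dyads per arm (Section 10.0), and the 20% attrition benchmark (Section 4.0), giving 64 × 0.8 = 51.2 dyads, or about 26 per arm. The correlation r between baseline and 1-month stress is an assumption, taken as 0.3, 0.5 and 0.7. The 95% CI half-widths for the arm difference, in SD units, are:

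- 1-month score alone: t(0.975; 2n − 2) × √(2/n)
- ANCOVA on baseline: t(0.975; 2n − 3) × √(2/n) × √(1 − r²)
- Change score: t(0.975; 2n − 2) × √(2/n) × √(2 − 2r)

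At n = 32, √(2/32) = 0.25 and t is about 2.00, so the 1-month score alone gives 2.00 × 0.25 = 0.50. ANCOVA at r = 0.5 gives 0.50 × √0.75 = 0.43.

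| Per arm | 1-month only | ANCOVA, r = 0.3 / 0.5 / 0.7 | Change score, r = 0.3 / 0.5 / 0.7 |
|---|---|---|---|
| 32 | 0.50 | 0.48 / 0.43 / 0.36 | 0.59 / 0.50 / 0.39 |
| 26 | 0.56 | 0.53 / 0.48 / 0.40 | 0.66 / 0.56 / 0.43 |

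With two time points, the time-by-arm test in a repeated-measures ANOVA is the change-score comparison. It beats the 1-month score alone only when 2 − 2r < 1, that is, when r > 0.5.

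**The case against.** The strongest reply is that nothing planned actually fails. Repeated-measures ANOVA is only one option beside regressions, the five repeated measures satisfy a sentence that does not say every measure, and the wording could mean separate arm comparisons at each time. This stands in part: the plan is not unworkable. But on the separate-comparisons reading the pre-treatment comparison of stress is still unavailable, and the text does not say that stress is an exception.

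Three stronger readings are tempting, and the documents do not support them.

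- *A reader might infer that chance imbalance in prior stress invalidates the 1-month comparison.* It does not. Randomisation makes the comparison unbiased, and its interval already allows for chance imbalance (SD of the baseline mean difference √(2/32) = 0.25 SD). Baseline stress simply cannot be checked or adjusted for directly, and the related baseline scores allow a partial check.
- *A reader might infer that Aim 3 sets out to test whether TOBI raises stress.* It offers elevated stress as a rationale, and Section 1.0 disclaims hypothesis testing.
- *A reader might convert r = 0.5 into 64/0.75 = 85 dyads' worth of precision.* That figure holds for ANCOVA with no attrition and against no adjustment at all. With 51.2 completers it is 51.2/0.75 = 68, and against adjustment for related scores the gain is smaller still.

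It is also fair that enrollment follows an acute burn, so a baseline score would reflect stress after the injury and not the caregiver's usual level. It would still precede randomisation and most outcomes, and those are the properties needed here. Finally, this is a secondary endpoint in a feasibility trial. That limits the stakes, although Section 6.0 counts testing the measurement among the purposes of such a trial.

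**Conclusion.** The point holds as a gap between the assessment schedule and the caregiver analysis plan. Pre/post arm differences can be estimated for five constructs and not for perceived stress. The losses are the change analysis, adjustment for baseline stress, and a stress score that precedes outcomes; the validity of the 1-month comparison is not among them. Under the assumed correlations, ANCOVA would cut the half-width by between 0.02 and 0.14 SD at 32 per arm (0.50 to 0.48, and 0.50 to 0.36). These figures rest on r, which the documents do not give, and on an unadjusted comparator; the increment over the distress and anxiety scores already collected cannot be quantified from the documents. No primary feasibility endpoint is affected. The change is worth making because it costs little.

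**What to change.** Add the Perceived Stress Scale to the baseline battery in Section 10.0 and to the enrollment column of the schedule table. That sitting already exists and comes before randomisation, so the score cannot be influenced by arm. In Section 11.0, specify ANCOVA of the 1-month score on arm and baseline score, which does not depend on r exceeding 0.5 to gain precision. The cost is a few minutes of caregiver time.

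If the extra questionnaire is refused, change the wording only. Analyse the 1-month score by ANCOVA with arm plus the baseline Peritraumatic Distress Inventory and PROMIS-Anxiety, and state that pre/post analyses are limited to the five measures taken twice. This needs no new data, but it leaves stress without a change analysis and without a measurement taken before outcomes.
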